18.6.2. HYPOGLYCEMIA ANALYSES

Hypoglycemia is a state produced by a lower than normal level of glucose in the blood. Hypoglycemia is classified as severe, documented symptomatic, asymptomatic, probable symptomatic, relative, nocturnal hypoglycemia. Patients will be instructed to record all hypoglycemic events in the patient's diary from Visit 2 until the EOT visit. The hypoglycemic events will be reviewed by the investigator and transcribed into the eCRF by the investigator or designee after the diary has been collected.

The classification will be derived as follows:

- Severe: the patients entered in the eCRF: "severe (external assistance required to resolve event)"
- Documented Symptomatic Hypoglycemia: the patient entered in the eCRF: symptomatic and checked the "glucose value was less than or equal to 70 mg/dL".
- Asymptomatic Hypoglycemia: the patient entered in the eCRF: asymptomatic (symptoms of hypoglycemia not present) and checked the "glucose value was less than or equal to 70 mg/dL".
- Probable Symptomatic Hypoglycemia: the patient entered in the eCRF: symptomatic and checked the "glucose was not measured".
- Relative Hypoglycemia: the patient entered in the eCRF: asymptomatic or symptomatic and checked the "glucose value was over 70 mg/dL".
- Nocturnal Hypoglycemia: the patient has any of the 5 types above and also checked the "Nocturnal" time of the event.

Hypoglycemia event rate per patient per 30 days calculated between two visits is defined as total number of episodes between two visits divided by the number of days between the visits, multiplied by 30 days. The baseline hypoglycemia period is defined from the run-in period until randomization day. This rate will also be calculated per patient for nocturnal hypoglycemia episodes.

Hypoglycemia event rate per patient per 30 days will be analyzed using the same MMRM model as for the primary efficacy parameter (without imputing any missing data).

For change from baseline of hypoglycemia rate, a graphical display at scheduled visits, of LSMeans

Document:	\sasdata\Mylan\Insulin_glargine\SYA22825\Biostatistics\Documentation\SAP\MYL-1501D-3004_SAP_Final_2_0_clean.doc		
Author:	[name]	Version Number:	2.0
		Version Date:	18OCT2018
Template No:	CS_TP_BS016 Revision 4	Reference:	CS_WI_BS005
Effective Date:	01Apr2016		

Analysis Plan Template

and 2-sided 95% CI will be generated from the MMRM model. Additionally, mean (+/- SD) for actual measurements by visit will also be presented.

In addition, nocturnal hypoglycemia rate and incidence will be analyzed in a same way as overall hypoglycemic episodes.

Listings of hypoglycemic episodes and severe hypoglycemic episodes will be presented by visit for each patient. If a sufficient number of severe hypoglycemic episodes are reported, then incidence summaries similar to the incidence of hypoglycemic episodes will be included.

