6.5.2.2.1 Classification

A. Severe Hypoglycemia

An event is considered as severe hypoglycemia if it requires the assistance of another person to actively administer carbohydrate, glucagon, or other resuscitative actions which results in neurological recovery, regardless of the availability of a blood glucose measurement. These episodes may be associated with sufficient neuroglycopenia to induce seizure or coma. Plasma glucose measurements may not be available during such an event, but neurological recovery attributable to the restoration of normal plasma glucose is considered sufficient evidence that the event was induced by a low plasma glucose concentration.

B. Documented Symptomatic Hypoglycemia

An event during which typical symptoms of hypoglycemia are accompanied by a measured plasma glucose concentration ≤ 70 mg/dL (3.9 mmol/L).

C. Asymptomatic Hypoglycemia

An event not accompanied by typical symptoms of hypoglycemia but with a measured plasma glucose concentration ≤ 70 mg/dL (3.9 mmol/L).

D. Probable Symptomatic Hypoglycemia.

Characteristic symptoms of hypoglycemia with no blood glucose level measurement that resolved with food intake, subcutaneous glucagon, or intravenous glucose.

E. Relative Hypoglycemia.

An event during which the subject reports any of the typical symptoms of hypoglycemia, and interprets the symptoms as indicative of hypoglycemia, but with a measured plasma glucose concentration > 70 mg/dL (3.9 mmol/L).

F. Nocturnal Hypoglycemia.

Nocturnal hypoglycemia will include hypoglycemia that occurs from the time the subject goes to bed at night till the time he or she wakes up. This may include any of the above 5 types of hypoglycemia.

Note: A diagnosis of severe hypoglycemia as per above classification will always be considered as serious adverse event. Other hypoglycemic episodes which fulfils ICH criteria for seriousness (life-threatening, hospitalization etc.) or represent important medical events based on investigator's judgment should also be reported to sponsor within 24 hours.

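### SAP 18.6.2 counts symptom-free entries over 70 mg/dL as relative (and, if ticked, nocturnal) hypoglycemia, which the protocol's categories do not allow and SAP 4.3 does not declare

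*SAP*

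**What the plan says.** Protocol V2.0 section 6.5.2.2.1 defines six categories, A to F. Two decide this point.

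- Relative (E): "An event during which the subject reports any of the typical symptoms of hypoglycemia, and interprets the symptoms as indicative of hypoglycemia", with measured glucose over 70 mg/dL.
- Asymptomatic (C): "An event not accompanied by typical symptoms of hypoglycemia but with a measured plasma glucose concentration" at or below 70 mg/dL.

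Nocturnal (F) overlays the other five: "This may include any of the above 5 types of hypoglycemia".

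SAP V2.0 section 18.6.2 derives the categories from eCRF boxes. For the relative category it writes "Relative Hypoglycemia: the patient entered in the eCRF: asymptomatic or symptomatic and checked the" box for a glucose value over 70 mg/dL. For nocturnal it writes "Nocturnal Hypoglycemia: the patient has any of the 5 types above and also checked the" nocturnal time box.

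Protocol 6.5.2.2 plans incidence by category. It also has nocturnal rate and incidence analyzed like overall episodes, and SAP 18.6.2 repeats this. SAP 4.3, where departures from the protocol are to be recorded, says there are none.

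**The concern.** The protocol can accept a relative event above 70 mg/dL because the subject had symptoms and took them for hypoglycemia. Once symptoms become optional, an entry can qualify with neither a symptom nor a low glucose value. Both documents introduce hypoglycemia as a state of lower-than-normal blood glucose, so such an entry has no basis in either.

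The outcomes at stake are relative incidence, nocturnal incidence and the nocturnal 30-day rate. A reader who sees that SAP 4.3 declares no changes would assume that the protocol's definitions lie behind those tables.

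**Working it through.** The check is a comparison of definitions. The plan gives no figure to reproduce.

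**Step 1: cross-classify non-severe entries.** Severe events are set apart in both documents, so only non-severe entries matter here.

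| Symptoms | Glucose | Protocol 6.5.2.2.1 | SAP 18.6.2 |
|---|---|---|---|
| Yes | 70 mg/dL or less | Documented symptomatic (B) | Documented symptomatic |
| No | 70 mg/dL or less | Asymptomatic (C) | Asymptomatic |
| Yes | Not measured | Probable symptomatic (D) | Probable symptomatic |
| Yes | Over 70 mg/dL | Relative (E) | Relative |
| **No** | **Over 70 mg/dL** | **None** | **Relative** |
| No | Not measured | None | None |

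The assigned class differs in one of the six cells.

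**Step 2: follow that cell into nocturnal.** The protocol and the SAP both build nocturnal from the five other types. The SAP's relative type is wider than the protocol's, so its nocturnal type is wider too. An entry from the fifth row with the nocturnal box ticked counts as nocturnal under the SAP only.

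**Step 3: see which outputs use it.** Relative incidence comes from the by-category summary in protocol 6.5.2.2. Nocturnal incidence and the nocturnal 30-day rate come from protocol 6.5.2.2 and SAP 18.6.2. No 30-day rate is planned for relative events.

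**Step 4: effect of a single entry, for illustration only.** The SAP rate is episodes divided by days between visits, times 30. I assume that consecutive scheduled visits are meant. One extra nocturnal entry in an interval of d days then adds 30/d to that subject's rate:

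- d = 7: 30/7 = 4.29
- d = 14: 30/14 = 2.14
- d = 21: 30/21 = 1.43
- d = 28: 30/28 = 1.07

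By the Study Week row of the schedule, the longest treatment-period gap is 21 days. Gaps of 28 days after randomization appear only in the Study Days row (day 42 to 70 and day 84 to 112), which does not agree with Weeks 9 and 15. Visit windows of ±3 and ±7 days mean that none of these values is a bound. The run-in, which SAP 18.6.2 takes as the baseline hypoglycemia period, is nominally 28 days. An entry there adds 1.07 to the subject's nocturnal baseline and lowers the change from baseline by the same amount.

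For incidence, one subject whose only relative or nocturnal entry is of this kind adds 1/101 = 0.99 percentage point to that arm, with the planned 202/2 = 101 per arm. The pool totals in SAP 8.2 sum to 219. At an even split of about 110 per arm (the split is not given), the figure is 1/110 = 0.91.

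The documents do not say how many such entries to expect. If there are none, every figure in this step is zero.

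**The case against.** The best defence is that such entries should rarely reach the derivation. Subjects record hypoglycemic events, and the investigator reviews them before they go into the eCRF (SAP 18.6.2). Full episode documentation under protocol 6.5.2.2.3 includes classification by the subtypes of 6.5.2.2.1, where an event without symptoms and with glucose over 70 mg/dL has no place. This stands as a reason to expect few entries or none. It does not correct the SAP line, which names asymptomatic entries expressly and would count any that arrive.

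Protocol section 7 also lets the SAP modify planned analyses. That stands too: a broader definition is permitted. What is missing is a declaration in SAP 4.3.

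A reader might go further in three ways that the documents do not support.

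- **The named safety endpoint is inflated.** Protocol 3.2.2.1 names the overall hypoglycemia rate and the incidence of hypoglycemic events. The SAP defines the overall rate by "Hypoglycemia event rate per patient per 30 days calculated between two visits is defined as total number of episodes between two visits" and does not say whether an entry outside every protocol category is an episode. An effect there is not shown.
- **The treatment comparison is biased.** The rule is prespecified and identical in both arms. Equal additions to both arms would leave the expected nocturnal rate difference unchanged. If an equal share q of otherwise event-free subjects had such an entry, an incidence difference would shrink by the factor (1 − q), but the documents give no value for q.
- **The SAP loosens the other categories as well.** The protocol's probable symptomatic category reads "Characteristic symptoms of hypoglycemia with no blood glucose level measurement that resolved with food intake, subcutaneous glucagon, or intravenous glucose", while the SAP line is "Probable Symptomatic Hypoglycemia: the patient entered in the eCRF: symptomatic and checked the" box for glucose not measured, with no mention of resolution. The relative line likewise omits the subject's own interpretation. Whether either condition is lost in the data depends on an eCRF that is not shown. Recovery and remedial measures are documented under protocol 6.5.2.2.3, and recording an event as hypoglycemic may itself imply the interpretation.

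**Conclusion.** The point holds and the SAP line is wrong as written. SAP 18.6.2 places in the relative category, and through it in nocturnal, a kind of entry that protocol 6.5.2.2.1 places nowhere, while SAP 4.3 says nothing has changed.

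Severity is minor. The exposed outputs are category breakdowns, no success criterion rests on them, and the primary HbA1c analysis does not use them. The size is unknown and may be nil. The per-entry figures above show only how one entry would act, and they rest on nominal visit intervals and a 1:1 split. The conclusion itself rests on the two definitions and on no assumed count.

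**What to change.** Before unblinding, do one of the following.

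1. In SAP 18.6.2, delete the words *asymptomatic or* from the relative line so that it agrees with protocol category E on symptoms. Add a sentence such as: Entries that meet none of protocol categories A to E will be listed and flagged, and will not be counted as relative or nocturnal.
2. If the broader relative definition is intended, keep the line and declare it in SAP 4.3 as a change from protocol 6.5.2.2.1, noting that it carries into nocturnal.

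The first option costs two deleted words, one added sentence and one flag in the derivation; the episode listing is already planned. The second costs one declaration. Neither needs new data.

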19. STUDY DATA TECHNICAL CONFORMANCE

The data will be submitted using the Clinical Data Interchange Standards Consortium (CDISC). The Study Data Tabulation Model (SDTM) data will use version 1.4 (SDTMIG). The derived datasets will follow the Analysis Data Model (ADAM) and will use version 1.1 (ADAMIG).

20. DATA NOT SUMMARIZED OR PRESENTED

Not applicable.

Document:	\\sasdata\Mylan\Insulin_glargine\SYA22825\Biostatistics\Documentation\SAP\MYL-1501D-3004_SAP_Final_2_0_clean.doc		
Author:	[name]	Version Number:	2.0
		Version Date:	18OCT2018
Template No:	CS_TP_BS016 Revision 4	Reference:	CS_WI_BS005
Effective Date:	01Apr2016		

APPENDIX 1. REPORTING CONVENTIONS

Page Layout:

The Section 14 tables and Appendix 16 listings should be in landscape orientation by default.

The output in Section 14 and Appendix 16 will be in RTF file format using Courier New font with 8 point size.

Statistical conventions:

The patient percentages (%) should be rounded to a whole number, with SAS rounding options used to obtain the values.

Percentages for values in the tables that are less than <1 should be presented as "<1".

If "%" is part of the column heading, do not repeat the "%" sign in the body of the table.

If a value is zero (0), then do not use 0% and leave the corresponding percentage blank.

The format for range should always be "Min, Max".

If there are missing data, then a missing row will be added to keep track of all patients. If there are no missing data, then delete the missing row. Percentages will not be presented on the missing category row.

Standard Deviation should be abbreviated as "SD", and Standard Error should be abbreviated as "SE"; it is presented within parenthesis next to the mean value, without any +/- sign. The Standard Deviation or Standard Error should have one additional decimal point beyond that of the mean (for example, if the mean has one decimal point, SD/SE should have two decimal points). Mean and median should have one additional decimal point beyond that of the data being summarized.

"N" will represent the entire treatment group, while "n" will represent a subset of the treatment group. For tables with population designated as a row heading, "N" should be used (i.e. tables where all the participant data is not available for every variable within a treatment group). As a guideline, if the number is used in denominator that it should be presented as "N". If the number is used in numerator it should be presented as "n".

P-values will be presented with 4 decimals.

Document:	\sasdata\Mylan\Insulin_glargine\SYA22825\Biostatistics\Documentation\SAP\MYL-1501D-3004_SAP_Final_2_0_clean.doc		
Author:	[name]	Version Number:	2.0
		Version Date:	18OCT2018
Template No:	CS_TP_BS016 Revision 4	Reference:	CS_WI_BS005
Effective Date:	01Apr2016		

APPENDIX 2. PARTIAL DATE CONVENTIONS

Imputed dates will NOT be presented in the listings.

ALGORITHM FOR TREATMENT EMERGENCE OF ADVERSE EVENTS:

START DATE	STOP DATE	ACTION
Known	Known	If start date < study med start date, then not TEAE If start date >= study med start date, then TEAE
	Partial	If start date < study med start date, then not TEAE If start date >= study med start date, then TEAE
	Missing	If start date < study med start date, then not TEAE If start date >= study med start date, then TEAE
Partial, but known components show that it cannot be on or after study med start date	Known	Not TEAE
	Partial	Not TEAE
	Missing	Not TEAE
Partial, could be on or after study med start date	Known	If stop date < study med start date, then not TEAE If stop date >= study med start date, then TEAE
	Partial	Impute stop date as latest possible date (i.e. last day of month if day unknown or 31st December if day and month are unknown), then: If stop date < study med start date, then not TEAE If stop date >= study med start date, then TEAE
	Missing	Assumed TEAE
Missing	Known	If stop date < study med start date, then not TEAE

Document: \sasdata\Mylan\Insulin_glargine\SYA22825\Biostatistics\Documentation\SAP\MYL-1501D-3004_SAP_Final_2_0_clean.doc

Author: [name]

Version Number:

2.0

Version Date:

18OCT2018

Template No: CS_TP_BS016 Revision 4

Reference: CS_WI_BS005

Effective Date: 01Apr2016

Analysis Plan Template

START DATE	STOP DATE	ACTION
		If stop date >= study med start date, then TEAE
	Partial	Impute stop date as latest possible date (i.e. last day of month if day unknown or 31st December if day and month are unknown), then: If stop date < study med start date, then not TEAE If stop date >= study med start date, then TEAE
	Missing	Assumed TEAE

ALGORITHM FOR PRIOR / CONCOMITANT MEDICATIONS:

START DATE	STOP DATE	ACTION
Known	Known	If stop date < study med start date, assign as prior If stop date >= study med start date and start date <= end of treatment, assign as concomitant If stop date >= study med start date and start date > end of treatment, assign as post study
	Partial	Impute stop date as latest possible date (i.e. last day of month if day unknown or 31 st December if day and month are unknown), then: If stop date < study med start date, assign as prior If stop date >= study med start date and start date <= end of treatment, assign as concomitant If stop date >= study med start date and start date > end of treatment, assign as post treatment
	Missing	If stop date is missing could never be assumed a prior medication If start date <= end of treatment, assign as concomitant If start date > end of treatment, assign as post treatment
Partial	Known	Impute start date as earliest possible date (i.e. first day of month if day unknown or 1 st January if day and month are unknown), then: If stop date < study med start date, assign as prior If stop date >= study med start date and start date <= end of treatment, assign as concomitant If stop date >= study med start date and start date > end of treatment, assign as post treatment

Document: \sasdata\Mylan\Insulin_glargine\SYA22825\Biostatistics\Documentation\SAP\MYL-1501D-3004_SAP_Final_2_0_clean.doc

Author: [name]

Version Number:

2.0

Version Date:

18OCT2018

Template No: CS_TP_BS016 Revision 4
Effective Date: 01Apr2016

Reference: CS_WI_BS005

Analysis Plan Template

START DATE	STOP DATE	ACTION
	Partial	Impute start date as earliest possible date (i.e. first day of month if day unknown or 1 st January if day and month are unknown) and impute stop date as latest possible date (i.e. last day of month if day unknown or 31 st December if day and month are unknown), then: If stop date < study med start date, assign as prior If stop date >= study med start date and start date <= end of treatment, assign as concomitant If stop date >= study med start date and start date > end of treatment, assign as post treatment
	Missing	Impute start date as earliest possible date (i.e. first day of month if day unknown or 1 st January if day and month are unknown), then: If stop date is missing could never be assumed a prior medication If start date <= end of treatment, assign as concomitant If start date > end of treatment, assign as post treatment
Missing	Known	If stop date < study med start date, assign as prior If stop date >= study med start date, assign as concomitant Cannot be assigned as 'post treatment'
	Partial	Impute stop date as latest possible date (i.e. last day of month if day unknown or 31 st December if day and month are unknown), then: If stop date < study med start date, assign as prior If stop date >= study med start date, assign as concomitant Cannot be assigned as 'post treatment'
	Missing	Assign as concomitant

Document: \sasdata\Mylan\Insulin_glargine\SYA22825\Biostatistics\Documentation\SAP\MYL-1501D-3004_SAP_Final_2_0_clean.doc

Author: [name]

Version Number:

2.0

Version Date:

18OCT2018

Template No: CS_TP_BS016 Revision 4
Effective Date: 01Apr2016

Reference: CS_WI_BS005

Analysis Plan Template

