9.2 Definitions

9.2.1 Adverse Events

An AE is defined as any untoward medical occurrence in a patient or clinical investigation patient administered a pharmaceutical product that does not necessarily have a causal relationship with the product. An AE can therefore be any unfavorable and unintended sign (including a new, clinically important abnormal laboratory finding), symptom, or disease, temporally associated with drug administration, whether or not related to the product.

The above definition covers also cases of

- Exacerbation of pre-existing diseases or conditions.
 - Pre-existing diseases or conditions will not be considered AEs unless there is an increase in the frequency or severity, or a change in the quality of the disease or condition.

An AE will be defined as a TEAE if the first onset (or worsening, in the case of pre-existing disease) is after the first administration of MYL-1501D after randomization through follow-up visit or 14 days after last dose [for subjects that do not have a follow-up visit].

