9.3 Management of Adverse Events

AEs or SAEs will be collected from the time the subject signs the informed consent form until the follow-up visit or 14 days after last dose of study medication. Pre-existing diseases or conditions (reported at visit 1 in medical history) will not be considered as AEs unless there is an increase in the frequency or severity, or a change in the quality of the disease or condition. An SAE deemed to be related to the study drug by the Investigator in consultation with sponsor will be reported even after the Follow-up visit if reported by subjects.

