9.3.2.5 Documentation

All AEs occurring within the period of observation for the study must be documented in the CRF with the following information; where appropriate (the period of observation for the study is described in [Section 6](#)):

- AE name or term in standard medical terminology.
- When the AE first occurred (start date and time); SAE start date is defined as the date the AE became serious.
- When the AE stopped (stop date and time or date and time of last observation if ongoing, i.e., recovering or not recovered).
- Severity of the AE.
- Seriousness criteria (hospitalization, death, etc.).
- Action taken with study medication as a result of AE.
- Outcome.
- Investigator’s opinion regarding the AE relationship to the study treatments.

Hypoglycemic events and associated signs/symptoms will only be recorded on the hypoglycemic episodes page of the CRF, unless they are SAEs (i.e., a severe episode).

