18.1. ADVERSE EVENTS

Adverse Events (AEs) will be coded using MedDRA central coding dictionary, Version 20.1.

An AE is defined as any untoward medical occurrence in a patient or clinical investigation patient administered a pharmaceutical product that does not necessarily have a causal relationship with the product. An AE can therefore be any unfavorable and unintended sign (including a new, clinically important abnormal laboratory finding), symptom, or disease, temporally associated with drug administration, whether or not related to the product.

The above definition covers also cases of:

Exacerbation of pre-existing diseases or conditions.

Pre-existing diseases or conditions (reported at time of screening in medical history) will not be

Document: \sasdata\Mylan\Insulin_glargine\SYA22825\Biostatistics\Documentation\SAP\MYL-1501D-3004_SAP_Final_2_0_clean.doc

Author: [name]

Version Number:

2.0

Version Date:

18OCT2018

Template No: CS_TP_BS016 Revision 4
Effective Date: 01Apr2016

Reference: CS_WI_BS005

Analysis Plan Template

considered AEs unless there is an increase in the frequency or severity, or a change in the quality of the disease or condition.

Events occurring in patients treated with the active comparator are also considered AEs.

An AE will be defined as treatment emergent (TEAE) if the first onset (or worsening in the case of pre-existing disease) is after randomization through follow-up visit or 14 days after last dose [for patients that do not have a follow-up visit].

See [Appendix 1](#) for handling of partial dates for AEs. In the case where it is not possible to define an AE as treatment emergent or not, the AE will be classified by the worst case; i.e. treatment emergent.

An overall summary of number of patients within each of the categories described in the sub-sections below, will be provided as specified in the templates.

Treatment group comparison will be performed using Fisher's exact test. P-value for the corresponding two-sided test will be presented.

Listings will include TEAEs and Non-TEAEs.

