18.1.1.1. Severity

Severity is classed as mild/ moderate/ severe/ life-threatening/ death (increasing severity). TEAEs starting on or after the first dose of study medication with a missing severity will be classified as severe. If a patient reports a TEAE more than once within that SOC/ PT, the AE with the worst case severity will be used in the corresponding severity summaries.

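### SAP V2.0 Appendix 2 has no worsening branch, so an AE recorded before the first MYL-1501D dose that worsens on it in the same record is never counted as a TEAE

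*SAP*

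**What the plan says.** SAP 18.1 defines the term: "An AE will be defined as treatment emergent (TEAE) if the first onset (or worsening in the case of pre-existing disease) is after randomization", with the window closing at the follow-up visit or, if there is none, 14 days after the last dose. Protocol 9.2.1 has the same clause but counts from the first MYL-1501D dose: "An AE will be defined as a TEAE if the first onset (or worsening, in the case of pre-existing disease) is after the first administration".

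SAP V2.0 Appendix 2 turns this into an algorithm for treatment emergence. When the start date is known it says "If start date < study med start date, then not TEAE", repeated for a known, a partial and a missing stop date. The start-date class "Partial, but known components show that it cannot be on or after study med start date" is also never a TEAE, whatever the stop date.

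SAP 18.1 has a worst-case fallback that assumes treatment emergence: "In the case where it is not possible to define an AE as treatment emergent or not, the AE will be classified" on that basis.

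Three recording rules in the protocol decide which start date reaches the algorithm:

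- Section 9.3 collects AEs from consent onward.
- Section 9.3 also says "Pre-existing diseases or conditions (reported at visit 1 in medical history) will not be considered as AEs unless there is an increase" (greater frequency or severity; a change in quality also counts).
- Section 9.3.2.5 asks for "When the AE first occurred (start date and time); SAE start date is defined as the date the AE became serious".

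**The concern.** The definition has two limbs, onset and worsening, and the algorithm implements only the first. A programmer who follows Appendix 2 cannot count a worsening on MYL-1501D if the AE record was opened during screening or the four-week run-in.

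This matters because every subject changes basal product from Lantus to MYL-1501D at randomization, and comparing local, systemic and other reactions between the two processes is a stated objective. A missed event drops out of the by-arm TEAE incidence, severity, drug-reaction, allergic-reaction and device-related tables. It stays in the listings and, if it began in run-in, in the non-TEAE summary (SAP 18.1.7). That summary gives no by-arm comparison, because SAP 6.2 presents the run-in population as one total.

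If such an event led to stopping MYL-1501D, it would be in neither AE discontinuation count. SAP 18.1.2 takes TEAEs only, and 18.1.7 counts withdrawals during run-in only. The discontinuation itself would still show in disposition (SAP section 10).

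**Working it through.** The plan gives no figure to reproduce. The check is to apply both rules to the same events.

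**Rows of the algorithm.** Four start-date classes × three stop-date classes = 12 rows. The known-start rows (3) and the partial-but-necessarily-pre-dose rows (3) make 6 rows that ignore both the stop date and any worsening when the start is pre-dose. The other 6 rows are not at issue: they rule out a TEAE only when the event ended before study drug, and otherwise count it.

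**The fallback.** It applies only when status cannot be determined. In the 6 rows above, the order of start and first dose is known, so it is never reached.

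**Both rules applied to eight kinds of event.**

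| Event | Recorded start | Appendix 2 | SAP 18.1 / protocol 9.2.1 |
|---|---|---|---|
| 1. Run-in AE, no worsening | Pre-dose | Not TEAE | Not TEAE |
| 2. New onset on MYL-1501D | On drug | TEAE | TEAE |
| 3. Medical-history condition, first worsens on drug | At worsening (protocol 9.3) | TEAE | TEAE |
| 4. Non-serious run-in AE that becomes serious on drug | Re-dated (protocol 9.3.2.5) | TEAE | TEAE |
| 5. Worsening on drug entered as a new record | On drug | TEAE | TEAE |
| 6. Medical-history condition that became an AE before first dose and worsens again on drug, same record | Pre-dose | Not TEAE | TEAE |
| 7. New run-in AE that worsens on drug, same record | Pre-dose | Not TEAE | TEAE only if pre-existing includes run-in AEs |
| 8. AE already serious before first dose, worsens on drug, same record | Pre-dose | Not TEAE | As 6 or 7, depending on medical history |

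The rules agree in rows 1 to 5. Row 6 contradicts the definition on any reading. Row 7 does so only on the broad reading. Row 8 shows that the gap is not confined to non-serious events: re-dating protects only an AE that first becomes serious on drug.

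**Can rows 6 to 8 arise?** They need the worsening to stay in the original record. Protocol 9.3.2.5 dates an AE from its first occurrence, and its list of AE fields has no worsening date. Table 5, used for AEs that CTCAE does not list, asks for one maximum intensity per AE. Both fit single-record entry, but neither prescribes it.

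**Size.** The documents give no rate for any of the steps. As an illustration only, for non-serious events of rows 6 and 7 together, assume:

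- 5% to 15% of subjects have a non-serious AE ongoing at first dose;
- 10% to 20% of those worsen;
- a share s of the worsenings stays in one record.

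The pool totals in SAP 8.2 sum to 13+9+13+19+16+9+10+12+29+37+13+8+23+8 = 219 subjects.

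- s = 0: 0 subjects.
- s = 0.5: 219 × 0.05 × 0.10 × 0.5 = 0.5 to 219 × 0.15 × 0.20 × 0.5 = 3.3.
- s = 1: 219 × 0.05 × 0.10 = 1.1 to 219 × 0.15 × 0.20 = 6.6.

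Row 6 alone is a subset. It needs a medical-history condition that worsened before first dose, was still open at first dose, worsened again on drug, and stayed in one record.

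**The case against.** **The appendix only handles partial dates, and 18.1 governs.** The appendix title supports this. But its first rows deal with fully known dates, its subheading presents it as the treatment-emergence algorithm, and the SAP does not say which text prevails.

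**A new run-in AE is not pre-existing disease.** This largely stands. SAP 18.1 itself ties pre-existing conditions to those reported in medical history at screening, and protocol 9.3 agrees. Protocol 7.5 also gives a shorter TEAE definition with no worsening clause. So row 7 is a case for better practice, not a contradiction. Row 6 is unaffected.

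**Sites may already open a new record.** This cannot be excluded. The SAP expects repeat records (18.1.1.1: "If a patient reports a TEAE more than once within that SOC/ PT, the AE with the worst case severity will be used"; 18.1.1.2 is similar), although neither section says that a worsening opens one. Protocol 9.5 makes test findings present at baseline that worsen on drug reportable as AEs. A second increase in a pre-existing condition can reasonably be read as a new AE with its own date. CRF completion guidance is not among the documents, so single-record entry is an inference.

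**The rule is the same in both arms.** True. The trial is double-blind and both arms switch from Lantus, so nothing in the documents points to a bias in either direction.

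**Conclusion.** A minor but real inconsistency. Appendix 2 cannot apply the worsening clause to an AE record opened before the first MYL-1501D dose. For a medical-history condition that became an AE in screening or run-in and worsens again on drug in the same record, the result contradicts SAP 18.1 and protocol 9.2.1. This holds whether the event is serious or not, unless it first becomes serious on drug and is re-dated.

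The number affected cannot be derived from the documents. It is zero if worsenings are entered as new records, and otherwise probably very few subjects. Only TEAE-based safety tables are affected.

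Three stronger readings are tempting and not supported:

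- A reader might infer that every worsening of pre-existing disease is lost. Rows 3, 4 and 5 show otherwise.
- A reader might take the top of the illustration, 6.6 of 219 (3.0%), as the size of the error. It rests wholly on assumed proportions, assumes that no site splits a record, and pools row 7 with row 6.
- A reader might extend the concern to the efficacy conclusion. The HbA1c non-inferiority test does not use TEAE status, and hypoglycemia is recorded on its own CRF page and analyzed separately.

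**What to change.** 1. Before lock and while blinded, list AEs that start before the first MYL-1501D dose and stop on or after it or are ongoing. Query each for a worsening on or after that dose and its date.
2. Amend both pre-dose rules in Appendix 2 (known start, and partial start that must be pre-dose) to: *not TEAE unless a worsening dated on or after the first MYL-1501D dose is recorded*. Naming that dose also settles the anchor. Appendix 2 does not define study med start, SAP 7.1 and 18.1 count from randomization, and protocol 6.2.1 also calls the run-in supply study medication.

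The second step depends on the first, because the AE fields in protocol 9.3.2.5 hold no worsening date. CRF guidance to split a record at worsening would also work, but only where follow-up remains. SAP V2.0 already lists randomized subjects by site, so it probably comes late.

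The cost is a few data queries and one amended rule. No new assessments are needed.
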